#### 4.4. Pharmacokinetic Evaluation

No pharmacokinetic analyses will be conducted.

### 4.5. Safety Analyses

Safety analyses will be conducted using the Safety population.

### 4.5.1. Study Drug Exposure

The cumulative amount of study drug exposure will be estimated by calculating the difference between the weight of the 4 bottles of drug at the time the drug was dispensed and the weight of the 4 bottles at the last visit. The amount of product used per day will be estimated by dividing the change by the number of days the subject was on treatment. These weights will be compared to the weight of the product that would be used if the subject was compliant with the protocol and used the spray 16 times per day (8 sprays BID) for 28 days.

Percent compliance will be summarized for each subject from date of first dose through the treatment period based on the net weight of the product administered. Net weight is calculated as the weight collected at Day 28 minus the weight at Day 1. Based on information provided by AOBiome, the expected amount of study drug used per week is approximately 15.68 g/week for 16 sprays/application per day.

Percent Compliance = 
$$\frac{(NetWeightofstudydrug)*100}{(2.24g/day*28daysoonstudy)}$$

The number of days the subject administered study drug, the amount of product used, and the percent compliance will be summarized by treatment group and presented in a by-subject data listing. The subject listing will also include by-visit IP weights. Percent compliance will be calculated only for subjects who returned the study drug at Day 28. In the listing, subjects who withdrew from the study early will be flagged.

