11.6.4 Week 2, 4 (Day 14, 28) study visit

- concomitant medications
- body weight

- obtain in clinic heart rate and blood pressure
- Oral hygiene questions
- EASI assessment
- VAS assessment
- Skindex 16 Questionnaire
- IGA scoring assessment
- obtain study medication weight for Investigational Product compliance
- collect study medication
- dispense investigational product to patient (Week 2)
- blood for biomarkers
- blood for clinical chemistry and hematology
- Microbial content (Week 4 visit only)
- study diary
- study counseling
- provide subjects with study cleanser and moisturizer (when necessary only)
- collect cleanser and moisturizer at Week 4 visit
- collect actigraphy watches returned by the subject at Week 4 visit
- recording of AEs if any
- skin swabs (Week 4 only)

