- 6. Weight of an IP kit will be obtained at the at the Baseline visit. Study staff will be asked to weigh 2 bottles without the carton box PRE FIRST DOSE. Weight will be recorded in grams. Subjects will be asked to bring both bottles back for the Week 2 and Week 4 visit. Upon return for the study visit, 2 bottles will be weighted again.
- 7. Subjects will be asked to apply the IP twice daily. First IP application will happen in the office under medical supervision.
- 8. AEs will be monitored throughout the trial, starting with the time ICF has been signed.
- 9. Cleanser and moisturizer should be returned to the study coordinator. Subjects will be asked to go back to their regular routine.
- 10. Actigraphy watch is dispensed at the Baseline visit. Subjects will be asked to wear one watch on each wrist starting at Baseline and through Day 28 visit. Subjects are allowed to take watches off during bathing/swimming/showering but will be asked to put watches back once these procedures are completed.
- 11. Patients should fast for at least 8 hours before the test. Blood for clinical chemistry will be shipped to the central lab for processing. Chemistry, Hematology, HbA1C, Lipid Panel and Angiotensin converting enzyme tests will be done at Screening, Week 2, Week 4 and Week 6. Serology will only be done at Screening. Kits and lab manuals will be provided by the Cenetron Labs.
- 12. Blood samples for biomarkers will be collected and processed on site within 5 minutes of collection. Patients should fast for at least 8 hours before the test. Samples will then be frozen onsite and shipped on monthly bases to the Central lab for storage.
- 13. Blood pressure readings will be obtained at every visit. Subject should be allowed to rest for > 5 minutes sitting, then serial clinic BP measurements and heart (x3) rate will be performed, using the non-dominant arm with a calibrated electronic sphygmomanometer. The average of the second and third readings will be documented.
- 14. Moisturizer to be used for the duration of the trial will be provided to all subjects starting with the Washout period. Subjects will be asked to refrain, if possible, from using any other moisturizer and apply the provided product while they are participating in the trial. Any left over moisturizer will be collected at Week 4 visit.

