#### Table 14.1.5.1A

# Summary of Drug Exposure (ITT Population)

Parameter	Statistic	B244	Placebo	Overall
raidmetei	Statistic	(N=xx)	(N=xx)	(N=xx)
Cumulative Study Drug Exposure (g) [1]	n	XX	XX	XX
	Mean (SD)	xx.x (xx.xx)	xx.x (xx.xx)	xx.x (xx.xx)
	Median	XX.X	XX.X	XX.X
	Min, Max	xx, xx	xx, xx	xx, xx
Amount of Product Used per Day (g) [2]	n	XX	XX	XX
	Mean (SD)	xx.x (xx.xx)	xx.x (xx.xx)	xx.x (xx.xx)
	Median	xx.x	xx.x	xx.x
	Min, Max	xx, xx	xx, xx	XX, XX
Days of Study Drug Administration	n	xx	xx	xx
	Mean (SD)	xx.x (xx.xx)	xx.x (xx.xx)	xx.x (xx.xx)
	Median	XX.X	XX.X	XX.X
	Min, Max	xx, xx	xx, xx	xx, xx
Percent Compliance [3]	n	xx	xx	xx
	Mean (SD)	xx.x (xx.xx)	xx.x (xx.xx)	xx.x (xx.xx)
	Median	XX.X	XX.X	XX.X
	Min, Max	XX, XX	XX, XX	XX, XX

 Cumulative study drug exposure = weight of the 4 drug bottles at last visit - weight of the 4 drug bottles at first dispense.

Source: /LMWLQII

DATE: HH:MM/DDMMMYYYY

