# Listing 16.2.4.1

# Demographics and Baseline Information

Treatment Group:

Subject Number	Age (years)	Sex	Race	Ethnicity	Height (metres)	Weight (kg)	BMI (kg/m^2)	Is Female Subject of Child- Bearing Potential?	If Yes, Form of Birth Control	If No, Reason
			American Indian or Alaska Native Asian Black or African-American Native Hawaiian or Other Pacific Islander White Other	Hispanic or Latino Not Hispanic or Latino Not Reported Unknown				Yes No	Condom (w/spermicide) Oral Patch Cervical Cap (w/spermicide) Vaginal Ring Vasectomized Partner Abstinence Diaphragm (w/spermicide) IUD Other	Post-Menopausal Surgically Sterile Hysterectomy Tubal Ligation Other, Specify

Confidential

Page 1 of x

DATE: HH:MM/DDMMMYYYY

Listing 16.2.4.2

Smoking History

Treatment Group:

Subject Number	Subject Have Smoking History	Type of Product Smoked	Date Subject Started to Smoke	Still Smoking?	Date Stopped Smoking	Number of Packs Per Day (Tobacco Products)	Number of Times Smoking Occurs per Week (non-tobacco products)
	Yes	Tobacco		Yes			
	No	Products		No			
		Non-Tobacco					
		Products					
		Both					

AOBiome Therapeutics

Confidential

Page 1 of x

Protocol ADB244-001

Listing 16.2.4.3

Medical History

Treatment Group:

Subject

Number

Medical History

Condition/Event

Description

MedDRA System Organ Class

Preferred Term

Date Diagnosed

Ongoing at Screening?

End Date

Currently Being Treated

DATE: HH:MM/DDMMMYYYY

with Concomitant

Medication?

Yes

No

Medical history is coded using MedDRA v20.0.

AOBiome Therapeutics

Confidential

Page 1 of x

DATE: HH:MM/DDMMMYYYY

Protocol ADB244-001

Listing 16.2.5.1

Dosing Data

Treatment Group:

Subject Number

Visit

Date/Time of Dispense (Rel Day)

Weight of Investigational Product (mg)

Rel Day = Relative to first dose of study medication, Day 1.

AOBiome Therapeutics Confidential Page 1 of x
Protocol ADB244-001

Listing 16.2.5.2

Extent of Exposure

Treatment Group:

Subject Baseline Weight Amount of Product

Number of Study Drug [1] Week 4 Weight (g) Used (g) [2] Expected Weight Percent Compliance [3]

 Cumulative study drug exposure = weight of the 4 drug bottles at last visit - weight of the 4 drug bottles at first dispense.

 Amount of product used per day = change / number of days the subject was on treatment.

 Percent compliance = (Net weight of study drug)/( Expected weight for 28 days of use)×100.

Confidential

Page 1 of x

Listing 16.2.6.1

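### SAP 4.5.1 subtracts the weights in the wrong order and, read literally, skips the Day 14 weights, so a fully compliant subject scores about -50% (or -100% on four bottles), never +100%

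*SAP*

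**What the plan says.** SAP 4.5.1 describes product use in two ways.

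- **Cumulative exposure** is the difference between "the weight of the 4 bottles of drug at the time the drug was dispensed" and their weight at the last visit. Footnote 1 of Table 14.1.5.1A turns this into a formula: "Cumulative study drug exposure = weight of the 4 drug bottles at last visit - weight of the 4 drug bottles at first dispense". Footnote 1 of Listing 16.2.5.2 repeats it.
- **Percent compliance** is 100 times net weight divided by 2.24 g/day times 28 days. For the numerator: "Net weight is calculated as the weight collected at Day 28 minus the weight at Day 1". It is limited: "Percent compliance will be calculated only for subjects who returned the study drug at Day 28".

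The expected weight is introduced as follows: "the expected amount of study drug used per week is approximately 15.68 g/week for 16 sprays/application per day". The same section elsewhere describes full compliance as 16 sprays a day, given as 8 twice daily.

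On collection, protocol 8.16 gives a kit of two bottles, each used for one week. Appendix A, footnote 6, says of Baseline: "Study staff will be asked to weigh 2 bottles without the carton box PRE FIRST DOSE". Protocol 11.6.4 has study medication collected at both visits and includes "dispense investigational product to patient (Week 2"). Protocol 8.17 requires weighing at every dispensing and every return, with the weights entered in the eCRF.

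SAP 2.1 admits to the Per Protocol population only subjects who administered at least half of the IP. It does not say how that is measured.

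**The concern.** There are two separate faults in the net-weight sentence.

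**Sign.** End weight minus start weight is negative when product is used. The order appears once in the text and again in two shell footnotes, so it is not a single slip. Only the opening sentence of 4.5.1 names the dispensed weight first, and it gives no formula.

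**Basis.** Kit 1 is weighed on Day 1 and handed back at Day 14. Kit 2 is handed out at Day 14 and returned at Day 28. Taken literally, the sentence subtracts a full kit 1 from a used kit 2 and ignores what was used in Weeks 1-2. Listing 16.2.5.2 fits this reading: its only weight columns before amount used are Baseline and Week 4.

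Percent compliance and product used are planned summaries by treatment group in the ITT, Safety and Per Protocol populations. Programmed as written, percent compliance is wrong for every subject who used product. Cumulative and per-day exposure take the wrong sign if programmed from the footnotes; days of administration is unaffected. If percent compliance is also what decides the 50% rule, Per Protocol membership is at risk. It is the only percentage-of-IP measure the SAP defines, but protocol 8.6 also puts missed doses in the eCRF, so the link is possible rather than stated.

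**Working it through.** **Inputs.** Expected use 15.68 g/week, 2.24 g/day in the denominator, 28 days (SAP 4.5.1). Two bottles per kit, one week per bottle, so 14 days per kit (protocol 8.16). Full-kit weights are not given in either document. Let D = full weight of kit 2 minus full weight of kit 1, and u = fraction of expected use in Weeks 3-4.

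**1. The plan's own figure.** 15.68 / 7 = 2.24 g/day, which reproduces. Denominator: 2.24 x 28 = 62.72 g. Per kit: 2.24 x 14 = 31.36 g.

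**2. Net-weight sentence read literally.** Score = 100 x (D - u x 31.36) / 62.72. Use in Weeks 1-2 does not enter.

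| Actual use | D = -4 g | D = 0 | D = +4 g |
|---|---|---|---|
| 100% throughout | -56.4% | -50.0% | -43.6% |
| 80% throughout | -46.4% | -40.0% | -33.6% |

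D = 0 and the range of 4 g either way are assumptions. If kit 2 is used for 12 to 16 days, as the visit windows of one day either way allow, full use with D = 0 gives -43% to -57%. For full use to score +100%, kit 2 would have to start 62.72 + 31.36 = 94.08 g heavier than kit 1, which is implausible for kits of two 30 ml bottles.

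**3. The literal measure does not rank subjects (D = 0).**
- No use in Weeks 1-2, full use in Weeks 3-4 (true compliance 50%): -31.36 / 62.72 = -50%, the same as a perfect user.
- Full use in Weeks 1-2, none afterwards (also truly 50%): 0 / 62.72 = 0%.

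**4. Four-bottle basis with the footnote order.** Full use gives -62.72 g in total, -62.72 / 28 = -2.24 g/day, and -62.72 / 62.72 = -100%. No kit-weight assumption is needed.

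**5. Reversing the sign only.** On four bottles, full use gives the correct +100%. On the literal reading with D = 0 it gives +31.36 / 62.72 = +50%, and half use gives +25%.

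**6. All four weights.** (Kit 1 dispensed - kit 1 returned) + (kit 2 dispensed - kit 2 returned) = 31.36 + 31.36 = 62.72 g, so +100% for full use and +50% for half use, whatever the full-kit weights.

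**7. If the 50% rule uses percent compliance as written.** On the literal reading, a score of 50% needs D - u x 31.36 to be at least 31.36 g, so even with u = 0 kit 2 would have to start 31.36 g heavier. On four bottles with the footnote order, no subject who used product could qualify.

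**8. Spray wording.** At 16 sprays a day, 2.24 g/day is 2.24 / 16 = 0.14 g per spray. At 16 sprays per application twice daily it is 2.24 / 32 = 0.07 g. The two wordings differ two-fold in implied weight per spray, so they must be reconciled before 62.72 g is relied on.

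**The case against.** The best reply is that the four-bottle reading is the natural one. The section opens on four bottles, the sentence before the formula speaks of product administered from first dose through the treatment period, and footnote 1 of Listing 16.2.5.2 attaches to its baseline weight column. On that reading only the sign is wrong, the size of every value is right, and a table of negative compliance would be noticed at once. Compliance enters no hypothesis test. Per Protocol is a supportive population, and SAP 2.2 provides a pre-unblinding review of major deviations, with the final deviation file, including IP-administration deviations, settled before hard lock. By-visit weights are already to be listed.

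Much of this stands. Intent can be inferred, the error is recoverable, and the Per Protocol consequence is conditional. It does not remove the fault. The net-weight sentence is silent on the number of bottles, no single weighing covers four bottles at first dispense, and the listing shell has no Day 14 weights. Someone who notices the negative values may simply reverse the sign, which on the literal reading leaves perfect users at +50%. The deviation review does not define the 50% measure either.

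The spray wording and the unit label in Listing 16.2.5.1 ("Weight of Investigational Product (mg"), where the protocol records grams) are minor and carry no weight in the conclusion.

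**Conclusion.** The concern holds; it should be fixed, but it does not threaten the main efficacy analysis. The stated rule gives a negative value for product used on either basis. The -100% figure assumes only use at exactly the expected rate. The -50% figure also assumes equal full-kit weights and an even 14/14-day split, and stays between about -44% and -56% for an assumed kit difference of up to 4 g. Which basis the SAP intends is not stated, and the choice decides whether a sign change alone is enough. The effect on Per Protocol membership depends on a link between percent compliance and the 50% rule that the documents neither make nor exclude.

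**What to change.** In SAP 4.5.1, replace the net-weight sentence with:

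- Amount used = (kit 1 dispensed at Baseline - kit 1 returned at Day 14) + (kit 2 dispensed at Day 14 - kit 2 returned at Day 28).
- Percent compliance = 100 x amount used / 62.72 g, for subjects who returned drug at Day 28, as now. State a rule for missing weights; setting the result to missing and flagging it when any of the four is absent is the simplest.

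Also:

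- Correct footnote 1 of Table 14.1.5.1A and of Listing 16.2.5.2 to dispensed minus returned, and add the Day 14 return and dispensing weights to that listing.
- Use grams in Listing 16.2.5.1.
- In SAP 2.1, name the measure behind the 50% rule (this one, or another such as diary doses) and say how it applies to a subject with a Day 28 visit but no percent compliance.
- Reconcile the two spray-count wordings behind 15.68 g/week.

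The cost is SAP and shell wording before database lock. Protocol 8.17 already requires all four weights, but the documents do not show the eCRF layout, so check that the Day 14 return and dispensing weights are held as separate fields.

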#### 4 5 2 Adverse Events

Adverse events will be analyzed in terms of treatment-emergent adverse events (TEAEs) which are defined as any AEs that begin or worsen on or after the start of study drug through 28 days after the last dose of study drug.

A treatment-related TEAE is defined as a TEAE that was considered by the Investigator to be at least possibly related to the study drugs.

If a subject experiences the same AE more than once with different toxicity grades, the event with the highest grade will be tabulated in the "by grade" tables. If a subject experiences multiple AEs under the same preferred term (SOC), the subject will be counted only once for that preferred term (SOC). In addition, AEs with a missing severity will be presented in the summary table as an intensity category of "Missing."

An overall summary table presenting the number of subjects who experienced the following will be presented by treatment arm: any TEAE, any related TEAE, any Grade 3 or 4 TEAE, any related Grade 3 or 4 TEAE, any serious TEAE, any serious related TEAE, any TEAE leading to discontinuation of treatment, any TEAE leading to study discontinuation, and any TEAE leading to death.

The incidence of TEAEs will be summarized by MedDRA SOC and preferred term. Tables summarizing the incidence of TEAEs will be generated for each of the following:

- x All TEAEs
- **X** TEAEs reported as treatment-related
- x Severe or Grade 3/4 TEAEs
- x Related Grade 3/4 TEAEs
- **▼** Serious TEAEs
- Related Serious TEAEs

If no subjects experience any of the events in the overall summary table, the corresponding table by SOC and preferred term will not be produced.

No formal hypothesis-testing analysis of AE incidence rates will be performed.

All AEs occurring on-study will be listed in subject data listings.

By-subject listings also will be provided for the following: subject deaths, serious AEs, and AEs leading to withdrawal.

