3 STUDY OBJECTIVES

3.1 Primary Objectives

• To evaluate the safety and tolerability of B244 in participants with mild to moderate Atopic Dermatitis.

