4 ENDPOINTS

4.1 Safety & tolerability:

• Safety and tolerability endpoints will consist of all adverse events reporting during the study duration.

4.2 Efficacy:

Difference in Atopic Dermatitis Area Severity Index (EASI) Score from Baseline to Day 28

4.3 Exploratory:

- Difference in Visual Analog Scale (VAS) Score for Pruritus from Baseline to Day 28
- Difference in the Skindex 16 Score from Baseline to Day 28
- Difference in the IGA score from Baseline to Day 28
- Difference in Actigraphy Movement Count per Hour and sleep quality during the night from Baseline to Day 28
- Difference in biomarkers between active and vehicle groups
- Composition of microbiome
- Difference in skin microbiota from baseline to Day 28 between active and vehicle groups
 - Observing a difference in Staphylococcus aureus and a more diverse microbial collection on the patient's skin.

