### 1.1.2. Study Objectives

#### 1.1.2.1. Primary Objectives

x To evaluate the safety and tolerability of B244 in subjects with mild to moderate Atopic Dermatitis.

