### 1.2.4.2. Safety Parameters

Safety and tolerability endpoints will consist of all adverse events (AEs) reported during the study duration from the date of randomization through 28 days after the last dose of study drug. Specific AEs are defined below.

Treatment-Emergent Adverse Events (TEAE): Any AE with onset after the first dose of study medication through 28 days after the last dose of study medication.

Serious Adverse Event (SAE): An AE occurring at any dose that results in any of the following outcomes: death, a life-threatening AE, in-patient hospitalization or prolongation of existing hospitalization, a persistent or significant disability/incapacity, or a congenital anomaly/birth defect.

Associated with Use of the Study Drug: There is a reasonable possibility that the experience may have been caused by the study drug. If the Investigator does not know whether or not study drug caused the event, then the event will be handled as "related to study drug" for reporting purposes. The determination of whether an AE is related to study drug is as follows:

- x Related: The AE has a missing, unknown, possible, probable or definite relationship to the study medication.
- x Not related: The AE is unlikely or definitely unrelated to the study drug.

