#### Table 14.3.1.1

# Overall Summary of Treatment-Emergent Adverse Events (Safety Population)

		B244		
	Statistic	(N=xx)	Placebo (N=xx)	(N=xx)
Subjects with at Least 1 Treatment-Emergent Adverse Event (TEAE)	n (%)	xx (xx.x)	xx (xx.x)	xx (xx.x)
Subjects with at Least 1 Treatment-Related TEAE	n (응)	xx (xx.x)	xx (xx.x)	xx (xx.x)
Subjects with at Least 1 Grade 3 or 4 TEAE	n (%)	xx (xx.x)	xx (xx.x)	xx (xx.x)
Subjects with at Least 1 Treatment-Related Grade 3 or 4 TEAE	n (응)	xx (xx.x)	xx (xx.x)	xx (xx.x)
Subjects with at Least 1 Serious TEAE	n (응)	xx (xx.x)	xx (xx.x)	xx (xx.x)
Subjects with at Least 1 Treatment-Related Serious TEAE	n (%)	xx (xx.x)	xx (xx.x)	xx (xx.x)
Subjects with at Least 1 TEAE that led to Treatment Discontinuation	n (%)	xx (xx.x)	xx (xx.x)	xx (xx.x)
Subjects with at Least 1 TEAE that led to Study Discontinuation	n (%)	xx (xx.x)	xx (xx.x)	xx (xx.x)
Subjects with 1 TEAE that led to Death				

If a subject experiences multiple occurrences in the category of Adverse event , the subject will be counted only once for that

PT/SOC.

If a subject experiences the same AE more than once with different CTCAE grades, the event with the highest grade will be tabulated.

TEAE is defined as any AEs that begin or worsen on or after the start of study drug through 30 days after the last dose of study drug.

Treatment-related TEAE is defined as TEAE that was considered by the Investigator to be at least possibly related to the study drug.

Severity will be graded based on the NCI CTCAE, Version 4.03.

Adverse events are coded using MedDRA v20.0.

Source: DIMMINIT

AOBiome Therapeutics Confidential Protocol ADB244-001

Page 1 of x

DATE: HH:MM/DDMMMYYYY

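### Safety is the only primary objective, yet the SAP plans no B244-minus-vehicle estimate or interval for any adverse event category

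*SAP*

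**What the plan says.** Protocol 3.1 gives one primary objective: "To evaluate the safety and tolerability of B244 in participants with mild to moderate Atopic Dermatitis". SAP 1.1.2.1 repeats it. EASI is the secondary objective; VAS, IGA, Skindex 16 and actigraphy are exploratory.

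The safety endpoint is broad. Protocol 4.1: "Safety and tolerability endpoints will consist of all adverse events reporting during the study duration". SAP 1.2.4.2 agrees and adds a time window.

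For the analysis, SAP 4.5.2 states "An overall summary table presenting the number of subjects who experienced the following will be presented by treatment arm" and lists nine categories: any TEAE, related, Grade 3 or 4, related Grade 3 or 4, serious, serious related, leading to treatment discontinuation, leading to study discontinuation, and leading to death. The same section says "No formal hypothesis-testing analysis of AE incidence rates will be performed". The shell of Table 14.3.1.1 has rows such as "Subjects with at Least 1 Treatment-Related TEAE" and "Subjects with at Least 1 TEAE that led to Treatment Discontinuation", with n (%) for each arm and a pooled column. It has no difference, ratio or interval. Protocol 15.3 and 15.4.2 likewise ask only for frequencies and incidence by arm.

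Between-arm intervals do appear, but only for efficacy. SAP 3.2 and 4.3.1 and Protocol 15.4.5 attach them to differences in treatment-group means.

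**The concern.** A concurrent vehicle arm lets adverse event incidence on B244 be read against a randomized comparator. As planned, the two percentages are printed side by side and nothing says how precisely their difference is known. The objective ranked first gets less statistical support than the objectives ranked below it.

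What is at stake is how the safety result is read. With arms of this size, similar percentages are compatible with a sizeable true excess. A reader shown 20% and 20% will tend to conclude that there is no difference. The more useful statement is how large an excess the data have not excluded, and the plan does not call for it.

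**Working it through.** **Inputs.** 130 randomized, 1:1, allowing for 20% dropout, with 52 per group needed (Protocol 15.1, SAP 3.1). The Safety population is everyone who received a dose (SAP 2.1). I assume all randomized subjects are dosed: 130 / 2 = 65 per arm. Neither document gives an adverse event rate, so incidences of 5% to 40% are assumptions.

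**The plan's own figure.** For EASI, the noncentrality is 3.9 / (7.0 × √(2/52)) = 2.841. With 102 degrees of freedom and one-sided 0.025, the t-test power is 0.803, and 51 per group gives 0.796. So 52 per group with more than 80% power reproduces, as does 104 / 0.8 = 130. This is the only sample-size calculation. No size or precision is stated for safety.

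**Precision of a risk difference.** With equal true incidence p in both arms, the approximate 95% half-width is 1.96 × √(2p(1−p)/65):

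| p | 2p(1−p)/65 | Half-width (points) |
|---|---|---|
| 5% | 0.00146 | ±7.5 |
| 10% | 0.00277 | ±10.3 |
| 20% | 0.00492 | ±13.8 |
| 30% | 0.00646 | ±15.8 |

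At 52 per arm the half-width for 20% would be ±15.4.

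**What the added column would show (Newcombe 95% intervals).** For 13/65, the Wilson limits are 12.1% and 31.3%. For 13/65 against 13/65 the difference is 0, and each limit lies √((0.200 − 0.121)² + (0.313 − 0.200)²) = 0.138 away, giving −13.8 to +13.8 points. For 20/65 on B244 against 13/65 on vehicle, the result is +10.8 points (−4.2 to +25.2). For 7/65 against 3/65 it is +6.2 (−3.6 to +16.4).

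**How often a true excess shows no observed excess.** Let X be the vehicle count and Y the B244 count, independent binomials with n = 65. I sum P(Y = j) × P(X ≥ j) over j:

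| Vehicle vs B244 (true) | B244 equal or lower | B244 strictly lower |
|---|---|---|
| 5% vs 15% | 3.5% | 1.7% |
| 10% vs 20% | 6.7% | 4.0% |
| 20% vs 30% | 11.0% | 7.7% |
| 30% vs 40% | 13.4% | 9.8% |

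In the 20% vs 30% case, ties make up the remaining 3.4%.

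**Zero events.** If no event of a given kind is seen among 65 subjects, the one-sided 95% upper bound on its rate is 1 − 0.05^(1/65) = 4.5%.

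**The case against.** The strongest reply is that descriptive adverse event reporting is usual in Phase II, and that protocol and SAP agree on it. The safety objective is worded as an evaluation of B244, while the wording that sets B244 against vehicle appears only in the efficacy objectives. No criterion for declaring the product safe is planned. Each cell gives n and %, so a reader can compute any interval. Safety also draws on laboratory and vital-sign summaries by arm and visit, and on routine blinded review by the safety committee (Protocol 18.3).

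Most of this stands. No planned analysis is wrong and no information is lost. But leaving the interval to the reader means that the report's own safety conclusion need not mention its uncertainty.

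The interval has limits too. In the 20% vs 30% case B244 shows a visible excess in 89% of trials, and the Newcombe interval would still include zero in about 74% (53% to 77% across the four cases above). It shows imprecision; it does not detect harm.

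Three stronger readings are tempting, and the documents do not support them.

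- A reader might infer that the report could rest a claim of safety on whichever overview row looks best. All nine rows are tabulated by arm, six tables by SOC and preferred term are specified, and deaths, SAEs and events leading to withdrawal are listed, so no row can be left out. Nor can one sensibly compute the chance that some row favours B244 by giving all nine the same rates: related events are nested within their parent rows, and the rows include death.
- A reader might infer that one row, such as any TEAE, should decide the conclusion. Protocol 16.1 counts exacerbation of a pre-existing condition as an AE, so atopic dermatitis flares can be TEAEs. A benefit on the disease could then offset a harm in that row.
- A reader might take the no-test sentence as the fault. A test is not needed. For 20% vs 30% at 65 per arm its two-sided power would be about 26%.

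**Conclusion.** The point holds as a reporting gap and a cheap improvement. The primary objective has no planned between-arm estimate or interval, so the report would not state an uncertainty of roughly ±10 to ±16 points for events with 10% to 30% incidence. A true 10-point excess would show no observed excess in about 3% to 13% of trials (11% for 20% vs 30%).

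These sizes rest on 65 treated per arm and on assumed incidences. With 52 per arm, the 20% vs 30% figure becomes 14%. The gap itself does not depend on these assumptions. The documents do not show that a favourable row could be selected, or that a test or a single deciding row is required.

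**What to change.** - Reconcile the TEAE window first. SAP 1.2.4.2 and 4.5.2 run to 28 days after the last dose; the footnotes of Tables 14.3.1.1 and 14.3.1.2 say 30. The column cannot be computed consistently until these passages agree.
- Add one column to Table 14.3.1.1: the B244-minus-vehicle risk difference with a two-sided 95% score interval (Newcombe or Miettinen-Nurminen) for each overview row. Label it descriptive and print no p-values.
- Keep the sentence in SAP 4.5.2 that rules out hypothesis testing, and add one that describes the new column.
- State that the safety conclusion will quote these intervals, including their upper limits.

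The cost is one column in an existing table and two sentences in the SAP, with no new data or patients. The downside is that wide intervals will make the safety statement look less certain than bare percentages do.
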